or not tolerated, patients will receive standard treatment from the study physicians following the protocol for treating malaria according to current Peruvians standards (see Available Alternative Treatment).

Back to Top

Safety Precautions: Describe the procedures for protecting against or minimizing any potential risks, *including risks of breach of confidentiality or invasion of privacy*. Where appropriate, discuss provisions for ensuring necessary medical or professional intervention in the event of adverse events, or unanticipated problems involving subjects. Also, where appropriate, describe the provisions for monitoring the data collected to ensure the safety of subjects. If vulnerable populations other than adults with impaired consent capacity are to be recruited, describe additional safeguards for protecting the subjects' rights and welfare.

Established antimalarial therapy will be given if a patient meets any of the following criteria:

1) Clinical decline or lack of clinical improvement or decrease in platelets by > 20% for Patients with a platelet count at inclusion of between 50,000/mm3 and 74,999/mm3 (thrombocytopenia grade 2) or a drop in platelet count to < 50,000/mm3 for

Patients with a platelet count of > 75,000/mm3 at inclusion, at 24 hours for P. vivax malaria and 12 hours for P. falciparum malaria Patients with a = 25% increase in parasitemia in comparison to baseline with or without fever.

2) Development of any clinical complications (WHO definition of complicated/severe malaria, WHO [2013])

3) Parasitemia > 100,000/µL for P. falciparum at any time with or without fever

4) Parasitemia > baseline (from the slides taken 30 min before start of treatment) with or without fever, 48 hours after first dose for P. vivax and 36 hours after first dose for P. falciparum

5) Failure to clear all parasites by microscopy associated with axillary fever > 37.5°C between 72 hours and 7 days for P. vivax and 60 hours and 5 days for P. falciparum

6) Failure to clear all P. vivax parasites by microscopy with or without fever on Day 7 and P. falciparum parasites by microscopy with or without fever on Day 5

7) Patient exhibits a rise of microscopically detectable parasitemia between Day 7 and Day 42 with or without fever

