Following discharge, the patient will be monitored as an out-patient every 3-4 days: (on Days 7, 10 or 11, 14, 17 or 18, 21, 24 or 25, 28, and 35) until the final clinic visit on Day 42. At each visit the patient will be accompanied by the health care professional to Clínica de la Asociación Civil Selva Amazónica (ACSA) in Iquitos for the following examinations:

• Physical examinations and body temperature measurements will be conducted at every visit (Days 7, 10 or 11, 14, 17 or 18, 21, 24 or 25, 28, 35, 42).

• Blood samples will be taken for parasitology (microscopy and qPCR) at every visit (Days 7, 10 or 11, 14, 17 or 18, 21, 24 or 25, 28, 35, and 42).

• Additional blood samples for hematology and clinical chemistry assessments will be taken on Days 7, 14, 28, 35, and 42. After discharge (negative microscopy), and during the 42 day follow up period, if a study subject displays parasitological signs (as confirmed by positive microscopy) or develops clinical signs of malaria, he/she will be given standard of care according to the national treatment guidelines and supervised by the investigator.

Patient data will be logged into an Electronic Data Capture system at site by the site. Where the data violate validation checks queries will fire within the system for the Investigator to address and respond. Medications will be coded using the WHO-drug dictionary. Medical conditions and AEs will be coded using the latest version of the MedDRA dictionary.

When data entry has been completed and all outstanding queries have been resolved for a CRF, the CRF will be eligible for QC checking. A sample of 9 (i.e. ?n + 1) Patients will be selected for QC checks and 100% of these Patients' data will be audited. In addition, 100% of demography, parasite count, AEs and withdrawal data will be checked for all Patients. The highest acceptable error rate for QC is 0.5%. A higher error rate will prompt a review of a further sample of 9 Patients. If the error rate remains above 0.5%, a 100% QC check of all data will be conducted.

All errors discovered will be corrected on the database and the corrections will be audit-trailed and will undergo a QC check. On satisfactory completion of the QC checks, the database will be locked.

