Benefit vs. Risk: Describe potential benefits to the subject(s); include potential benefits to society and/or general knowledge to be gained. Describe why the risks to subjects are reasonable in relation to the anticipated benefit(s) to subjects and in relation to the importance of the knowledge that may reasonably be expected to result. If you are using vulnerable subjects (e.g., impaired consent capacity, pregnant women, etc...), justify their inclusion by describing the potential benefits of the research in comparison to the subjects' vulnerability and the risks to them. For information about inclusion of certain vulnerable populations, see the IRB/ORI Standard Operating Procedure for Protection of Vulnerable Subjects [C3.0100] [PDF].

Malaria is a devastating disease inflicting high social and economic impact worldwide. To combat increasing levels of drug resistance, the WHO recommends combinations of artemisinin derivatives, the most potent and rapidly acting anti-malarial agents available, with long-acting antimalarials (ACT) for the treatment of uncomplicated P. falciparum malaria (e.g. Coartem® (artemether-lumefantrine), Eurartesim® (dihydroartemisinin-piperaquine), artesunate-mefloquine, etc.). Mutations continue to emerge that mediate resistance to artemisinin, delay parasite clearance upon artemisinin treatment, and may ultimately lead to treatment failures, suggesting artemisinin resistance is rapidly becoming a global issue. In addition, emerging cases of resistance to piperaquine in combination with dihydroartemisinin in Cambodia (unpublished results) as well as undesired side effects of mefloquine underline the need for development of a novel, safe, rapidly acting antimalarials, not subject to current resistance mechanism.

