Each cohort will consist of two treatment arms. Cohort progression for each treatment arm will be managed independently of the other treatment arm. For example, if data from the *P. falciparum* cohort (1A) do not meet the success criteria or are inconclusive, but the data from the *P. vivax* cohort (1B) do meet the success criteria, then the *P. vivax* arm may continue to explore reducing levels of SJ733 exposure according to Figure 1 (cohort 2B and 3B), while the *P. falciparum* initial cohort of the study will be expanded or terminated. Established antimalarial therapy will be given if a patient meets any of the defined treatment failure criteria. Finally, if one treatment arm meets the failure criteria, remaining patients who have not received treatment may be reassigned to the other treatment arm to improve statistical power.

Study Population

Men and women between the ages of 18 and 70 years with *P. falciparum* or *P. vivax* malaria monoinfection living in Peru. 2-6 cohorts of adult patients (10 patients per cohort) with acute, uncomplicated *P. falciparum* or *P. vivax* malaria monoinfection. In total, there will be a minimum of 20 and a maximum of 60 patients.

3. Data Elements

Endpoints

Primary endpoints related to efficacy

For *P. vivax:* Crude Adequate Clinical and Parasitological Response (ACPR) at Day 14 defined as the absence of microscopically determined parasitemia (thick smear) on Day 14, irrespective of axillary temperature, in patients who did not previously meet any of the criteria of early treatment failure, late clinical failure, or late parasitological failure.

For *P. falciparum:* Crude Adequate Clinical and Parasitological Response (ACPR) at Day 14 defined as the absence of microscopically determined parasitemia (thick smear) on Day 14, irrespective of axillary temperature, in patients who did not previously meet any of the criteria of early treatment failure, late clinical failure, or late parasitological failure.

Success criterion: Crude ACPR on Day $14 \ge 80\%$ (equivalent to $\le 20\%$ recurrence).

Primary endpoints related to safety and tolerability up to Day 42

- Incidence, severity, drug-relatedness, and seriousness of adverse events
- Proportion of patients with clinically significant abnormal laboratory values including changes from baseline (biochemistry and hematology)
- Proportion of patients with clinically significant abnormal vital signs including changes from baseline

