The primary efficacy endpoints will be summarized descriptively, across the two cohorts and by the two cohorts. A statistical test will not be performed on the Crude ACPR on Day 14. Achieving a rate of 80% will be the decision rule for cohort dose phase. For future study planning, a one-sample z-test will be used to compare the rate of success, as defined by the Crude ACPR on Day 14, to the hypothesized rate of 80%.

Secondary efficacy variables will be summarized descriptively (by cohort; on Days 0, 14, 42) with proportions, means, and medians. To inform future studies, all estimates will be presented with 95% confidence intervals ($1.96 \pm$ margin of error). Graphical summaries will be used to describe changes in efficacy endpoints over time.

Exploratory Analysis

Exploratory model-based analyses will be performed as data allows. These will include model-based analyses of PK, PD and PK/PD.

Safety Analysis

Adverse events (AEs) will be summarized in Listing 9: Cumulative Summary of Adverse Events. The listing will include the following information: Patient ID, AE Description, Start Date, Stop Date, Special Interest, Severity, Relationship to Study Drug, Action Taken, Outcome of AE, Expected AE, and if the AE was a Serious Adverse Event (SAE).

Laboratory values that fall outside a clinically accepted reference range must be evaluated and commented on by the Investigator and graded according to the DMID Toxicity Scale for Determining Severity of Adverse Events (Protocol Attachment 3, Section 8.1.2).

All related AEs, AEs with outcome death, AEs leading to permanent discontinuation of treatment, SAEs and related SAEs will be summarized in Listing 10: Cumulative Summary of Serious Adverse Events. The listing will include the following information: Patient ID, Age, Sex, Dose, SAE Description, Start Date, Stop Date, SAE Category, and Relationship to Study Drug.

Treatment related AEs are those rated by the Investigator as "definite", "probable", "possible". In case relationship is unknown or missing the worst case will be assumed and the AE will be considered to be drug related

Planned Interim Analyses

Interim analyses will be made to review parasite reduction, adverse events, and clinical laboratory data. Following review, a decision on cohort progression will be made. However, as this is an exploratory study no formal analyses with adjustments for type I error are planned.

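### The Day 42 safety proportions that carry no causality step are not separated at rescue, so rescue-drug effects can enter an SJ733 cohort's figures, more so in less effective cohorts

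*Combined protocol and SAP*

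**What the plan says.** SAP section 3 (Endpoints) heads its safety list "Primary endpoints related to safety and tolerability up to Day 42". The list holds two kinds of endpoint. Adverse events are described by incidence, severity, seriousness and relationship to drug. The rest are plain proportions of patients: clinically significant laboratory or vital-sign abnormalities, falls in hemoglobin, low neutrophils, Hy's law and other liver flags, skin reactions, raised methemoglobin and ECG changes. These proportions involve no judgement of cause.

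Rescue falls inside that window. The SAP's Study Design section says: "Established antimalarial therapy will be given if a patient meets any of the defined treatment failure criteria". The IRB application, under Safety Precautions, lists triggers that start within the first day. The last one is: "Patient exhibits a rise of microscopically detectable parasitemia between Day 7 and Day 42 with or without fever". For recurrence after discharge, the same section says "he/she will be given standard of care according to the national treatment guidelines and supervised by the investigator". The regimens, under Available Alternative Treatment(s), are artesunate-mefloquine plus primaquine for P. falciparum and chloroquine plus primaquine for P. vivax.

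Safety sampling continues: "Additional blood samples for hematology and clinical chemistry assessments will be taken on Days 7, 14, 28, 35, and 42". No exception is made for rescued patients, and Data Collection places methemoglobin among these safety tests.

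On analysis, SAP section 4 (General Approach) reports observed data by dose cohort and sets baseline at the last value before study medication. It announces analysis sets but does not go on to define them. The only planned output on rescue is Listing 8, known from its title alone.

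**The concern.** A laboratory value that becomes abnormal after a patient has started another antimalarial is still compared with the pre-SJ733 baseline and still counted in that patient's SJ733 cohort. The more a regimen fails, the more of its patients carry a second drug exposure. The safety comparison between regimens is then partly a comparison of their failure rates.

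That comparison is one of the trial's purposes. The SAP expects roughly five-fold higher exposure in Cohort 1 than in Cohort 2, and it justifies optional Cohort 3 partly by better tolerability. If lower exposure brings more failures, rescue-drug effects fall mainly on the low-exposure cohorts and could hide a real exposure-toxicity gradient. The IRB application itself refers, as general background under Benefit vs. Risk, to "undesired side effects of mefloquine". It gives no rate.

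**Working it through.** **Figures in the plan.** The plan states no safety event rate, safety precision or rescue-drug rate, so there is no safety figure to reproduce. Its one power statement concerns efficacy: 80% against 98%, n = 20, one-sided 0.05. It reproduces as Φ((0.18 − 1.645 × √(0.8 × 0.2/20)) / √(0.98 × 0.02/20)) = 0.853. Nothing proposed here changes it.

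**Patients rescued.** Primary analyses pool the two parasite arms within dose, giving 20 patients per dose cohort (SAP, Sample Size Justification). The decision thresholds are ACPR 80% and 60% at Day 14 (SAP, Study Design).

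- ACPR 80%: 20 × 0.20 = 4 patients failing, hence rescued, by about Day 14.
- ACPR 60%: 20 × 0.40 = 8 patients.

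Recurrences between Day 14 and Day 42 add to both.

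**Assumptions.** Let q be the probability that a rescued patient develops a given flagged abnormality because of the rescue drugs. The documents give no value, so q is taken from 5% to 30%. It could differ between species, because the regimens differ. Rescued patients are assumed to stay in safety follow-up, and the true SJ733 rate is set to zero.

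**Points added to the cohort proportion** = m × q / 20, where m is the number rescued. **Chance of at least one such patient** = 1 − (1 − q)^m.

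| q | m = 4: points added | m = 4: chance of ≥1 | m = 8: points added | m = 8: chance of ≥1 |
|---|---|---|---|---|
| 5% | 1 | 19% | 2 | 34% |
| 10% | 2 | 34% | 4 | 57% |
| 20% | 4 | 59% | 8 | 83% |
| 30% | 6 | 76% | 12 | 94% |

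**Effect on a comparison.** Take one cohort at 80% ACPR and another at 60%, with the same q and no difference in SJ733 toxicity. The spurious difference is (0.40 − 0.20) × q, which is 1 to 6 points. One patient in 20 is 5 points, so this is 0.2 to 1.2 patients on average.

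**Person-time.** If rescue is at Day 14, the share of the 42 days spent after rescue is 4 × 28/(20 × 42) = 13.3%, or 8 × 28/(20 × 42) = 26.7%. This shows how much follow-up is affected. It does not measure bias, because the endpoints are proportions of patients.

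**The case against.** The strongest reply is that the important decisions are already protected, and much of this stands. A reader might infer that rescue-drug adverse events are simply counted against SJ733, and that a rescue-drug SAE could readily help fail a cohort. The documents do not support that:

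- The investigator rates each adverse event's relationship to study drug (SAP, Safety Analysis).
- The investigator must always assess causality for an SAE, and the report collects concomitant medication (Data and Safety Monitoring).
- The SRT and DSMB have the final say on SAE relatedness (Benefit vs. Risk).
- Failure on safety needs two incidents of the same drug-related SAE (SAP, Study Design).
- Progression is judged at Day 14, so only rescue before then can touch it.

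The SAP does add a default: "In case relationship is unknown or missing the worst case will be assumed and the AE will be considered to be drug related". Given the mandatory SAE assessment, it should rarely apply to SAEs.

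Three further limits stand. The outpatient schedule lists no ECG, so contamination of the ECG endpoint after discharge is not shown. No passage says outright that rescued patients remain in safety follow-up. The detailed clinical protocol is attached by name but is not in the text available, so a rule there cannot be excluded.

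It can also be argued that an all-data summary is a defensible conservative choice in a small descriptive study, with AE start dates listed and liver tests plotted by patient. That justifies keeping the summary. It does not remove the need for a split, because the proportions themselves still mix the two periods. If rescued patients instead leave follow-up, the Day 42 proportions rest on unequal observation between cohorts, so the SAP needs a rule either way.

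**Conclusion.** The point holds for the safety proportions without an attribution step: laboratory, liver, hemoglobin, neutrophil, methemoglobin, skin and vital signs. As the SAP is written, abnormalities first seen after rescue count in the SJ733 cohort, more often where efficacy is lower. The size is 1-6 percentage points with 4 of 20 rescued and 2-12 points with 8 of 20. This rests on an assumed 5-30% event rate per rescued patient, on continued follow-up after rescue, and on no later failures. It is a cheap improvement to the analysis, and the trial's decision rule does not depend on it.

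A reader might go further and conclude that only pre-rescue data should support the tolerability statement. That does not follow. Cutting follow-up at efficacy failure gives less effective cohorts less time at risk, so they could look safer for the opposite reason. In the Phase 1b study described under Potential Risks, ALT above five times the upper limit occurred where recrudescence was early and rapid, so a cut at rescue could also discard abnormalities emerging around failure.

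**What to change.** In SAP section 4 (Safety Analysis):

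- Keep the all-data summary to Day 42.
- Record the start date of definitive antimalarial treatment as an analysis variable, and confirm that Listing 8 carries it.
- For each safety endpoint, add a column restricted to observations before that date, by dose cohort, with person-time at risk beside it.
- Flag each adverse event and each abnormality as first seen before or after rescue.
- State whether rescued patients remain in safety follow-up, and how they enter the announced analysis sets.
- State that regimen comparisons read the two columns together.

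The cost is one date, one flag and one extra column. Treatment, sample size and efficacy power are unchanged. The downside is that follow-up in the restricted column is shorter and depends on efficacy. Endpoints such as ALT elevation lasting more than 4 weeks cannot be assessed there for early failures and should be marked so.

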
9) Women of child-bearing potential, has a negative pregnancy test at screening, and agrees to comply with one of the following during the treatment stage of the study and for a period of 30 days after stopping study drug:

a. Use of oral, implantable, or injectable hormonal contraceptive, either combined or progestogen alone used in conjunction with barrier method as defined below.

b. Use of an intrauterine device with a documented failure rate of <1% per year.

c. Barrier method consisting of either condom or diaphragm.

d. Male partner who is sterile prior to the female subject's entry into the study and is the sole sexual partner for that female.

e. Complete abstinence from intercourse for 2 weeks prior to administration of study drug, throughout the study and for a period of 30 days after stopping study drug.

Exclusion Criteria:

1) Signs and symptoms of severe/complicated malaria according to the World Health Organization Criteria 2010 (Attachment 1: Definition of Severe Malaria)

2) Mixed Plasmodium infection.

3) Severe vomiting, defined as more than three times in the 24 hours prior to inclusion in the study, or severe diarrhea defined as 3 or more watery stools per day.

4) Severe malnutrition (defined as the weight-for-height being below -3 standard deviation or less than 70% of median of the NCHS/WHO normalized reference values)

5) Presence of a significant medical or psychiatric condition, or any other serious or chronic clinical condition requiring hospitalization, or any other condition that in the opinion of the investigator precludes participation in the study.

6) Female patients must not be either lactating or pregnant as demonstrated by a negative serum point-of-care pregnancy test predose (the result of the pre-dose assessment must be confirmed negative prior to dosing).

7) Employment under the direct supervision of the investigators or study staff.

8) Clinically significant alterations to hematologic or clinical chemistry parameters that in the opinion of the investigator precludes participation in the study, including:

a. AST/ALT > 3 x upper limit of normal range (ULN) and total bilirubin is normal

b. AST/ALT > 2 x ULN and total bilirubin is >1 and <1.5 x ULN and conjugated bilirubin is > 35% of the total bilirubin

c. Total bilirubin > 1.5 x ULN

d. Serum creatinine levels > 2 x ULN

e. Hb level < 8 g/dL

f. Platelet level < 50,000/mm3

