• Proportion of patients with a decrease in hemoglobin (Hb): > 2 g/dL from baseline to an absolute value of < 5 g/dL

- Proportion of patients with an absolute Neutrophil count $< 1,000/\mu$ L after baseline
- Proportion of patients meeting Hy's law criteria
- Proportion of patients with the following LFT changes:
 - Any ALT or $AST \ge 5 \times ULN$
 - Any AST or ALT ≥ 3 x ULN together with the appearance of fatigue, nausea, vomiting, right upper quadrant pain or tenderness, fever, rash and/or eosinophilia (eosinophil percent or count above the ULN)
 - Persistent ALT $\ge 3 \text{ x}$ ULN for a period of more than 4 weeks.

• Proportion of patients with clinical signs of possible cutaneous adverse reactions such as dermatitis, rash, erythematous rash, macular rash, papular rash, maculo-papular rash, pruritic rash, pustular rash, vesicular rash

• Proportion of patients with clinically significant increases in venous methemoglobin levels

• Proportion of patients with significant changes in ECG findings, including heart rate, ECG intervals (PR, QTcB, QTcF), conduction changes or abnormalities

Success criterion: No repeated drug-related serious adverse events (Attachment 3, Section 8.1.2).

Secondary Endpoints

Secondary endpoints related to malaria signs and symptoms up to Day 42

- Proportion of patients with symptoms or physical examination signs related to uncomplicated *P. vivax* or *P. falciparum* malaria (dizziness, headache, nausea, anorexia, vomiting, diarrhea, pruritus, urticaria, skin rash, abdominal pain, joint pain, muscle pain, palpitations, sleep disturbance, confusion, hearing disturbance, visual disturbance, fatigue)
- Fever Clearance Time as defined as the time from baseline to the first of two consecutive post-dose axillary temperature measurements < 37.5°C obtained within an interval of 4 to 24 hours of each other.

Secondary endpoints related to secondary treatment outcomes

- Crude ACPR at Days 28, 35, and 42 (*P. vivax* or *P. falciparum*)
- Recurrence (*P. vivax* or *P. falciparum*) up to Day 42

Secondary endpoints related to parasite clearance kinetics by microscopy

- Parasite clearance time (PCT)
- PRR (parasite reduction rate) and parasitemia half life
- Times to microscopic clearance of asexual parasites
 - Total reduction (PC100)
 - 99% reduction (PC99)
 - 90% reduction (PC90)
 - 50% reduction (PC50)
- Microscopically determined percentage reduction in asexual parasites from baseline at:

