The overall study design is to demonstrate proof of concept and serves as an exploratory study. It is not intended to demonstrate superiority or non-inferiority against a control. Rather the goal is to establish preliminary data for planning future studies and to assess whether the SJ733 is safe and the observed curative rate equals or exceeds 80%. As such, there will be no statistical testing of hypotheses. This exploratory Proof of Concept study uses a fixed clinical safety and parasitological responses (primary endpoints) defined as the absence of any drug-related SAE or microscopically determined parasitemia 14-days after initiation of therapy in \geq 80% patients who did not violate any of the inclusion/exclusion criteria.

General Approach

The overall study design involves two cohorts receiving SJ733 doses (600 mg and 300 mg) with and without cobicistat (150 mg) as cohorts. Data subsets (eligible, evaluable and completer) will be used in the potential comparisons.

The primary analytic approaches will be descriptive. All data will be summarized descriptively for the appropriate analysis sets defined below: Continuous variables by descriptive statistics (number of patients [n], mean, standard deviation [SD], minimum, median, maximum); categorical data by absolute and relative frequencies (n and %) or contingency tables.

While this is a proof of concept, exploratory study, any potential comparisons between dose cohorts will be informative. Potential longitudinal data will be described as graphical summaries presented by each group. Unless indicated otherwise, summary statistics will be reported for observed data only, by dose cohort. Missing data will not be imputed. If a baseline value is missing, no change from baseline will be calculated.

Baseline is defined as the last observation prior to the administration of study medication.

SAS v9.4 or higher will be used for all analyses and a significance level of 0.05 will be used for all statistical tests.

Primary Analysis (Efficacy)

Primary analyses will be conducted across the two cohorts and by the two cohorts. Estimates will be presented with 95% confidence intervals.

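### In the haemoglobin safety endpoint the fall from baseline is redundant given the entry limit, so the line counts only Hb below 5 g/dL and gives no count of falls above 2 g/dL that end higher

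*Combined protocol and SAP*

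**What the plan says.** SAP section 3 (Data Elements), under the primary endpoints for safety and tolerability up to Day 42, lists the proportion of patients with a decrease in Hb of "> 2 g/dL from baseline to an absolute value of < 5 g/dL". The word joining the two parts makes both necessary.

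Four other provisions bear on it:

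- **Entry limit.** The IRB application (Study Population, exclusion criterion 8e) excludes "Hb level < 8 g/dL". The lead-in to criterion 8 reads "Clinically significant alterations to hematologic or clinical chemistry parameters that in the opinion of the investigator precludes participation in the study, including", followed by the numeric limits.
- **Baseline.** SAP section 4, General Approach: "Baseline is defined as the last observation prior to the administration of study medication".
- **General laboratory endpoint.** The same primary safety list includes "Proportion of patients with clinically significant abnormal laboratory values including changes from baseline (biochemistry and hematology", with no numeric Hb limit.
- **Grading.** SAP section 4, Safety Analysis: "Laboratory values that fall outside a clinically accepted reference range must be evaluated and commented on by the Investigator and graded", using the DMID toxicity scale. Adverse events go into Listing 9.

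Section 5 of the SAP adds a clinical laboratory table and figures of Hb over time.

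**The concern.** The endpoint is worded as a change from baseline, but among patients who meet the entry limit it measures no change. It is a single absolute cut-off. The higher a patient's starting Hb, the more that patient can lose without being counted on this line.

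This matters because the line is a named primary safety proportion in a trial meant to supply data for planning later studies, and because red-cell effects are evidently of interest. The application reports reversible methemoglobinemia in dogs and plans methemoglobin monitoring and G6PD testing in P. vivax patients. The SAP plots methemoglobin, haptoglobin, LDH and reticulocytes. A reader of the final report could take a zero on this line to mean that no patient had a large Hb fall, which the line cannot show.

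**Working it through.** The plan states no figure for this endpoint, so there is none to reproduce. The check is an inequality.

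**Inputs**

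- B = baseline Hb, the last pre-dose value (SAP section 4, General Approach). Entry requires B ≥ 8 g/dL (exclusion criterion 8e).
- V = a post-baseline Hb value.
- Event as written (SAP section 3): B − V > 2 **and** V < 5.

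**Step 1: does the fall condition ever matter?** If B ≥ 8 and V < 5, then B − V > 8 − 5 = 3, which exceeds 2. Every value that meets the second condition already meets the first.

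Enumeration agrees. Taking B from 8.0 to 18.0 and V from 2.0 upwards in 0.1 g/dL steps (assumed grid limits, which do not affect the logic), there are 101 × 30 = 3,030 pairs with V < 5. All 3,030 also have a fall above 2 g/dL.

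**Step 2: when would it matter?** It needs V < 5 together with B − V ≤ 2, so B ≤ V + 2 < 7. The baseline would have to be below 7 g/dL, more than 1 g/dL under the entry limit.

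**Step 3: what fall is needed to count?** It must exceed B − 5.

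| Baseline (g/dL) | Fall must exceed (g/dL) | As % of baseline | Falls above 2 g/dL not counted |
|---|---|---|---|
| 8 | 8 − 5 = 3 | 37.5 | above 2, up to 3 |
| 10 | 10 − 5 = 5 | 50.0 | above 2, up to 5 |
| 12 | 12 − 5 = 7 | 58.3 | above 2, up to 7 |
| 14 | 14 − 5 = 9 | 64.3 | above 2, up to 9 |

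Examples of falls that are not counted on this line:

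- 14.0 to 5.1 g/dL: fall 8.9, and 8.9 / 14.0 = 64%.
- 12.0 to 5.0 g/dL: fall 7.0, and 7.0 / 12.0 = 58%.

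**Step 4: is there another fixed-threshold count of falls?** Setting the other provisions side by side:

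- The general laboratory endpoint is a patient-level proportion and names change from baseline, but it rests on clinical significance without a stated Hb limit.
- DMID grading applies to values outside the reference range. The grades are in Protocol Attachment 3, which is not among the documents available here.
- The descriptive summaries give n, mean, SD, minimum, median and maximum. A minimum can show the worst value, but not how many patients had a large fall.
- The Hb figures show change over time without a count. Figures 21a and 21b are both titled for females, apparently a typing error; as printed, no male Hb figure is listed.

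**The case against.** The strongest reply is that a redundant clause changes no count and contradicts nothing. The line may simply be a severe-anaemia endpoint, and nothing in the documents says that a fall above 2 g/dL was meant to be counted alone. Large falls have other routes into the report: the general laboratory endpoint in the same list, investigator comment and DMID grading, adverse event incidence and Listing 9, the laboratory table and the figures. The line also drives no decision. The safety success criterion and the progression guidelines use repeated drug-related serious adverse events, and the interim review looks at laboratory data as a whole.

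Most of this stands, and it rules out three stronger readings that a reader might infer:

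- **That the trial would record a fall from 14 to 5.1 g/dL as no event.** This is true of this one line only; the other routes can capture it.
- **That the line gives false reassurance to the trial's decisions.** The progression rule does not use it.
- **That the line will almost surely read 0%.** The documents give no expected rate. If the per-patient risk of Hb below 5 g/dL were assumed to be 0.1% to 1%, the chance of 0 in 20 patients would be 0.999^20 = 98% to 0.99^20 = 82%; for 60 patients it would be 94% to 55%. The answer depends on the assumption.

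A separate defence is that criterion 8 is qualified by investigator opinion and that baseline may be later than the screening value, so a baseline under 8 g/dL is conceivable. It does not help unless the baseline is below 7 g/dL.

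What the reply does not remove is that the other routes visible in the SAP work through judgement, grading or description. None is a proportion of patients with a fall beyond a stated size.

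**Conclusion.** The point holds as a matter of wording and reporting, and it is minor. Given the entry limit, the fall component has no effect and the endpoint is the same as Hb below 5 g/dL. Falls above 2 g/dL that end at 5 g/dL or higher are not counted on this line; depending on baseline, that covers falls of up to 3 g/dL (from 8) to 9 g/dL (from 14).

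This rests on two conditions. The pre-dose baseline must be 7 g/dL or higher, which the entry limit all but ensures. The statement that no other fixed-threshold count exists is limited to the text available: the DMID grades and the definitions of adverse events of special interest sit elsewhere and may contain an Hb threshold. The documents do not show that large falls would be missed by the trial as a whole, or that cohort progression would be affected.

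**What to change.** In the safety reporting, most naturally the clinical laboratory summary (Table 4), show two separate proportions overall and by cohort:

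1. patients with a fall in Hb of more than 2 g/dL from baseline at any post-baseline visit up to Day 42;
2. patients with any post-baseline Hb below 5 g/dL.

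Keep the composite as a third line if it is wanted. State the denominator for each: the first needs a baseline and at least one later value, since the SAP calculates no change when baseline is missing; the second needs only a later value. Both thresholds are already in the plan, so no new limit is proposed and no further data are needed. The sponsor should also reconcile the endpoint wording with the entry limit and, if only the composite was intended, say so.

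The cost is one or two extra table lines and possibly a less favourable figure, because the first proportion cannot be lower than the composite.
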